7.11 Additional Visits as Required

- Pain Score
- Concomitant Medications (including injectable narcotics)
- Average Daily Narcotic Dose for Prior Month
- Weight
- Quality of life
- Adverse Event/Device Event Assessment
- Pancreatic Duct Imaging, as applicable

7.12 Study Completion

Patients who receive the WallFlex Pancreatic stent will be followed for 6 months after initial stent removal or 6 months after observation of complete distal migration. See Section 4.3 (secondary endpoint bullet #3) for directions regarding restenting of recurrent strictures.

Additional visits may be conducted at the Investigator's discretion in accordance with Adverse Event or Device Event data collection. A patient will be considered lost to follow-up if the patient remains unresponsive to communication after three documented attempts by study staff.

7.13 Source Documents

Table 7.133-1: Source Documentation Requirements

Requirement	Disposition
Imaging before and after study stent placement	Retain at center
Imaging after study stent removal	Retain at center
Imaging 6 months after stent removal/observation of complete distal migration	Retain at center

The Investigator/institution guarantees direct access to original source documents, including cholangiogram and/or imaging documentation, by BSC personnel, their designees, and appropriate regulatory authorities. In the event that the original medical records cannot be obtained for a patient that is seen by a non-study physician at a non-study institution, photocopies of the original source documents must be made available for review.

August 28, 2017

Boston Scientific
WallFlex Pancreatic Pivotal Protocol
91067616 Rev/Ver AK
Page 31 of 64

8 Statistical Considerations

8.1 Endpoints

8.1.1 Primary Endpoint

Primary Effectiveness Endpoint:

Pain Reduction

Pain reduction will be assessed at 6 months post-stent removal or 6 months post-observation of complete or partial stent migration compared to pain collected at baseline. Baseline for patients without a plastic pancreatic stent immediately prior to study stent placement will be at the time of enrollment. Baseline for patients with a plastic pancreatic stent immediately prior to study stent placement will be at the time of study stent placement.

Pain will be scored between 0 and 100 as the mean of the VAS Pain Score and Frequency of Pain sectors of the Izbicki pain scale.

Complete pain relief is defined as pain score ≤ 10 , and partial pain relief is defined as pain score > 10 and reduced by at least 50% compared to baseline.

Complete or partial pain relief in the setting of a 50% higher average daily narcotic dose will be considered a primary effectiveness endpoint failure. Average daily narcotic dosage for prior month will be assessed at baseline visit prior to plastic or study stent placement, whichever is implanted first, and at 6 months post-stent removal/observation of complete distal migration.

Patients who experience stent migration in setting of recurring pain (VAS Pain Score of ≥ 20) will be considered as having failed the primary effectiveness endpoint.

Patients who are restented in the setting of recurring pain will be considered as having failed both the primary effectiveness endpoint and the secondary stricture resolution endpoint and may only be restented with a non-study stent.

Restenting with a new study stent may only occur during the initial stent placement procedure for such situations as stent misplacement, improper stent size choice, or other conditions, as necessary and will not be considered a primary effectiveness endpoint failure or a secondary effectiveness stricture resolution endpoint failure.

For the patients who have a single plastic stent in place for up to 90 days before receiving the study stent, inclusion criteria #6 and #7 will be reassessed immediately prior to the plastic to study stent exchange. Patients who do not meet the inclusion criteria levels of the VAS pain score (≥ 20) and frequency of pain score (50, 75, or 100) at the time of stent exchange will be excluded from the primary effectiveness endpoint analyses but will be included in the primary safety endpoint analysis and all secondary endpoint analyses. For the patients who meet the inclusion criteria levels, we will use the scores (VAS Pain Score and Frequency of Pain Score) collected immediately prior to the plastic to study stent exchange as their baseline and include them in the primary effectiveness endpoint analyses.

Primary Safety Endpoint:

August 28, 2017

Boston Scientific
WallFlex Pancreatic Pivotal Protocol
91067616 Rev/Ver AK
Page 32 of 64

Rate of related Serious Adverse Events (SAEs) from WallFlex Pancreatic stent placement to end of study.

Relatedness will be determined by the PI, reporting if the SAE is related to the study stenting procedure, to the indwelling study stent, to study stent removal and/or to study stent migration.

Pain thought to be caused by WallFlex Pancreatic stent expansion will be reported, but will not count towards the endpoint if all three of the following conditions apply:⁵

1. Pain can be managed by medication, with the exception of injectable narcotic use for more than 24 hours.
2. Pain does not cause WallFlex Pancreatic stent removal.
3. Pain resolves by 72 hours after WallFlex Pancreatic stent placement.

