Study Visits and Follow-Up Schedule	
 Baseline Visit: Demographics, Medical History, Symptom Assessment including Pain Score, Concomitant Medications (including injectable narcotics), Average Daily Narcotic Dose, Weight, Quality of Life Score, EPS History, Adverse Events, Imaging (if applicable). If ESWL is deemed necessary at Baseline visit, patient may receive a plastic pancreatic stent placed for 30 to 90 days before study stent placement at the discretion of the Investigator, for example, if there is concern about stone fragments of stone sludge in side branches of the pancreatic duct. WallFlex Pancreatic Stenting Procedure: Pre-stenting pancreatic stone clearance (if applicable), Pancreatic Duct Imaging or other imaging, WallFlex Pancreatic Stent Placement, EPS (if required), Pain Score (prior to stent procedures), Weight, Concomitant Medications (including injectable narcotics), Average Daily Narcotic Dose, Quality of Life, Adverse Events, Plastic Stent Removal prior to study stent placement, as applicable Indwell Follow-up via Telephone or in Person on Month 1 and Month 3: Pain Score, Concomitant Medications (including injectable narcotics), Average Daily Narcotic Dose, Weight, Quality of Life Score, Adverse Events Study Stent Removal(s) intended after 6 months of stent indwell: Pain Score prior to Stent Removal, Concomitant Medications (including injectable narcotics), Average Daily Narcotic Dose, Stent Removal Procedure(s), Weight, Quality of Life Score, Adverse Events, Pancreatic Duct imaging or other imaging to assess stricture resolution Post-Removal Follow-up via Telephone or in Person 3 months after stent removal or observation of complete distal migration: Pain Score, Concomitant Medications (including injectable narcotics), Average Daily Narcotic Dose, Weight, Quality of Life Score, Adverse Events Post-Removal Follow-up via Telephone or in Person 6 months after stent removal or observation of complete distal migration: Pancreatic Duct Imaging or other Imaging, Pain Score, Concomitant Medications (including injectable narcotics), Average Daily Narcotic Dose, Weight, Quality of Life Score, Adverse Events OPTIONAL: If a naso-pancreatic drain is placed after stent removal, then repeated pancreaticographic assessment of stricture resolution at 24 to 72 hours post stent removal. Additional visits as needed

August 28, 2017

Boston Scientific
 WallFlex Pancreatic Pivotal Protocol
 91067616 Rev/Ver AK
 Page 7 of 64

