5.1 Inclusion Criteria

Patients who meet all of the following criteria may be given consideration for inclusion in this clinical investigation, provided no exclusion criterion is met.

1. Age 18 or older
2. Willing and able to comply with study procedures and follow-up schedule and provide written informed consent to participate in study
3. Chronic pancreatitis induced stricture of Cremer Type IV, namely distal dominant stricture with upstream ductal dilation.
4. For patients with a prior plastic pancreatic stent: VAS Pain Score and Frequency of Pain sectors of the Izbicki pain scale at the time of placement of the plastic stent.
5. Availability of narcotic dosage for at least one month prior to baseline visit for patients who do not have a prior plastic pancreatic stent or availability for one month prior to placement of prior plastic pancreatic stent, where applicable.
6. VAS Pain Score of ≥ 20 before study stent placement for patients without a prior plastic pancreatic stent. VAS Pain Score of ≥ 20 before initial plastic pancreatic stent placement for patients with a prior plastic pancreatic stent indwelling for 90 days or less before study stent placement. VAS Pain Score is captured via Izbicki pain scale.
7. Pain occurring weekly or more frequently (assessed by Frequency of Pain sector of the Izbicki pain scale) as reported before study stent placement for patients without a prior plastic pancreatic stent, or before placement of initial plastic pancreatic stent for patients with a prior plastic pancreatic stent indwelling for 90 days or less before study stent placement.
8. Minimum 5 mm diameter of dilated duct immediately upstream of pancreatic duct stricture
9. Prior clearance of pancreatic stones where needed
 - If pancreatic duct stone clearance prior to placement of the study stent includes ESWL, then a plastic pancreatic stent may be placed immediately after the ESWL procedure at the discretion of the Investigator, for example, if there is concern about stone fragments or stone sludge in side branches of the pancreatic duct, and may be left indwelling for 30-90 days.

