 - If new pancreatic duct stones requiring ESWL have formed by the time of intended study stent placement, then the patient will not receive the study stent and be excluded from the study. Further treatment of the patient will be provided per standard of practice outside of the study. In case the study stent is not placed during the same session in which the plastic stent is removed, the pain score needs to be collected again prior to study stent placement.
10. Prior endoscopic pancreatic sphincterotomy (EPS), historically or to be provided at time of SEMS placement as applicable

August 28, 2017

Boston Scientific
 WallFlex Pancreatic Pivotal Protocol
 91067616 Rev/Ver AK
 Page 23 of 64

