6.1 Patient Status and Classification

6.1.1 Enrolled Cohort

A patient is considered “enrolled” after signing the study-specific Informed Consent Form (ICF). Patients who sign the ICF but subsequently do not meet one or more of the selection criteria will be considered screen failures and excluded from the study.

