7.6.2 Assessments

- Pain Score (prior to stent procedures)
- Weight
- Concomitant Medications (including injectable narcotics)
- Average Daily Narcotic Dose for Prior Month

August 28, 2017

Boston Scientific
WallFlex Pancreatic Pivotal Protocol
91067616 Rev/Ver AK
Page 29 of 64

- Quality of Life
- Pancreatic Duct Imaging (pre-and post-procedure)
- EPS (if required, per section 2.2)
- Plastic Stent Removal prior to study stent placement, as applicable
- Study Stent Placement Procedure
- Adverse Event/Device Event Assessment

7.7 *Stent Indwell Follow-Up: Month 1 (30 days ± 5 days) and Month 3 (90 days ± 10 days) – Telephone or Office/Hospital Visit*

- Pain Score
- Concomitant Medications (including injectable narcotics)
- Average Daily Narcotic Dose for Prior Month
- Weight
- Quality of Life
- Adverse Event/Device Event Assessment

7.8 *Study Stent Removal Visit: Month 6 (180 days ± 15 days) – Office/Hospital Visit*

- Pain Score (prior to stent removal)
- Concomitant Medications (including injectable narcotics)
- Average Daily Narcotic Dose for Prior Month
- Weight
- Quality of Life
- Study Stent Removal
- Adverse Event/Device Event Assessment
- Pancreatic Duct Imaging
- OPTIONAL: Pancreatogram 24-72 hours post-stent removal, in case a naso-pancreatic drain was left in place after stent removal.

7.9 *Post-Stent Removal Follow-Up: Month 3 (90 days±15 days post-removal) – Telephone or Office/Hospital Visit*

- Pain Score
- Concomitant Medications (including injectable narcotics)
- Average Daily Narcotic Dose for Prior Month
- Weight
- Quality of Life
- Adverse Event/Device Event Assessment

7.10 *Post-Stent Removal Follow-Up: Month 6 (180 days±15 days post-removal) – Telephone or Office/Hospital Visit*

- Pain Score
- Concomitant Medications (including injectable narcotics)

August 28, 2017

Boston Scientific

WallFlex Pancreatic Pivotal Protocol

91067616 Rev/Ver AK

Page 30 of 64

- Average Daily Narcotic Dose for Prior Month
- Weight
- Quality of Life
- Adverse Event/Device Event Assessment
- Pancreatic Duct Imaging

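### A patient who has ESWL after enrolment and no plastic stent at study stenting keeps the pre-ESWL pain score as baseline, so relief from ESWL can count towards the study stent's responder rate

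*Combined protocol and SAP*

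**What the plan says.** Section 8.1.1 (also Section 4.1 and the synopsis) sets two baselines for the primary effectiveness endpoint:

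- No plastic stent: "Baseline for patients without a plastic pancreatic stent immediately prior to study stent placement will be at the time of enrollment". Section 6.1.1 defines enrolment as signature of the consent form.
- Plastic stent: "Baseline for patients with a plastic pancreatic stent immediately prior to study stent placement will be at the time of study stent placement".

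Section 8.1.1 then adds a safeguard for patients with a single plastic stent in place for up to 90 days. Criteria 6 and 7 (VAS and pain frequency) are reassessed just before the exchange. Those below the levels leave the primary effectiveness analyses; the others take the pre-exchange scores as baseline.

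Two provisions create pathways that these rules do not cover well:

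- ESWL without a plastic stent. Criterion 9 in Section 5.1 says that after ESWL "a plastic pancreatic stent may be placed immediately after the ESWL procedure at the discretion of the Investigator". The synopsis visit schedule agrees: "If ESWL is deemed necessary at Baseline visit, patient may receive a plastic pancreatic stent". Both are permissive.
- A plastic stent removed in an earlier session. Criterion 9 continues: "In case the study stent is not placed during the same session in which the plastic stent is removed, the pain score needs"; the rest of that sentence asks for a fresh score before the study stent goes in. It does not say what that score is used for.

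Sections 7.1 and 7.6.2 schedule a pain score for every patient at the placement visit, before stent procedures.

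**The concern.** The safeguard for exchange patients keeps relief obtained before the study stent out of the stent's responder rate. ESWL is also a treatment that may relieve pain before the study stent is placed, but the safeguard is triggered by the plastic stent and not by the intervening procedure. A patient with staged ESWL and no plastic stent therefore falls under the enrolment rule, although a later pre-stent score exists.

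The trial has one arm and a fixed 53% performance goal, so no concurrent control would absorb relief that came from ESWL. Two patients with identical scores can also be classified differently, depending only on an investigator's discretionary choice about a temporary plastic stent.

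**Working it through.** **1. The plan's own figure.** Inputs from Section 8.1.2 and the synopsis: goal 53%, assumed rate 75%, exact test, one-sided alpha 0.025, power 80%, n = 43. By the exact binomial, n = 43 rejects at 30 or more responders, with error 0.0190 at 53% and power 0.834 at 75%. At n = 42 power is 0.766. The 43 reproduces and is not affected by this point.

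**2. How the rule classifies one patient (scores assumed).** The pain score is the mean of VAS and frequency.

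- Enrolment: (70 + 75)/2 = 72.5
- After ESWL, before the study stent: (30 + 50)/2 = 40
- Six months after removal: (15 + 50)/2 = 32.5

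Reduction from enrolment: 1 − 32.5/72.5 = 55%, which is partial relief. Reduction from the pre-stent score: 1 − 32.5/40 = 19%, which is not. An exchange patient with these scores passes the re-check (VAS at least 20, frequency 50), takes 40 as baseline and is a non-responder. The ESWL patient without a plastic stent is a responder unless another failure rule applies.

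**3. Possible effect on the test.** The documents give neither quantity below, so both are assumed:

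- f = share of effectiveness patients who, measured from enrolment, are already responders at placement: 5%, 10%, 15%.
- s = probability that such a patient ends as a success: 75%, or 100% as the ceiling.

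The true rate for everyone else is set at the goal, so the observed rate is p = 0.53(1 − f) + s·f. For s = 75%, p = 0.541, 0.552, 0.563. For s = 100%, p = 0.5535, 0.577, 0.6005.

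One-sided error is P(X ≥ r) with X binomial(n, p). I use n = 43 (r = 30) and n = 57 (r = 39). Section 8.1.2 plans for 64 patients who meet the pain levels, and 64 less the 10% allowance is about 57 (64 × 0.9 = 57.6).

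| n | f = 0 | s = 75%: f = 5 / 10 / 15% | s = 100%: f = 5 / 10 / 15% |
|---|---|---|---|
| 43 | 1.9% | 2.7 / 3.7 / 5.0% | 3.9 / 7.2 / 12.5% |
| 57 | 1.3% | 2.0 / 2.9 / 4.2% | 3.1 / 6.5 / 12.3% |

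**4. Whether another planned analysis would reveal it.** Section 8.1.3 addresses missing data only. The subgroups in Section 8.2.3 are gender, narcotic use and prior multiple plastic stents. Section 8.2.1 summarises ESWL history descriptively. No analysis by ESWL status or on another baseline is pre-specified.

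**The case against.** **The affected group is narrow.** The footnote in the Section 7.1 schedule ties stone clearance at the Baseline visit to patients who receive a plastic stent; the only other mark is at the placement visit. Prior stone clearance is itself an entry criterion, so ESWL may precede consent, and then the enrolment score already reflects it. Baseline and placement may also fall on the same day. This stands as a limit on size. It does not close the pathway, because criterion 9 keeps the plastic stent optional.

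**Criterion 6 may already require pain at placement.** It asks for VAS of at least 20 before study stent placement, and Section 8.1.2 plans for 64 patients who meet the levels at that time. But criterion 6 does not say after ESWL, and the formal re-check in Section 8.1.1 covers plastic-stent patients only. Even on the stricter reading, the baseline value would still be the enrolment score.

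**Early relief is not yet success.** The endpoint falls 6 months after removal of a stent meant to stay 6 months. Restenting for recurring pain, migration with VAS of at least 20, and a 50% higher narcotic dose all count as failure. A reader might infer that these patients are successes before the stent is placed, or that 3.1–12.3% is the expected error. Neither follows: that range needs every early responder to persist for about a year, and is a ceiling.

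**The goal may carry the same relief.** The 53% comes from plastic-stent series. Whether they scored baseline before or after stone clearance cannot be seen from the documents, so bias relative to the goal is possible but not shown. The unequal treatment of similar patients within this trial does not depend on that.

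**Conclusion.** The point holds for staged ESWL after enrolment with no plastic stent at study stenting. There the stated rule uses a pre-ESWL baseline and omits the re-check that the plan applies to exchange patients.

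For a plastic stent removed in an earlier session, a reader might infer that the enrolment score is definitely the baseline, because no stent is in place immediately beforehand. The documents do not settle this: criterion 9 requires a fresh score, and Section 8.1.1 does not say which score counts. That case is an ambiguity to resolve.

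The size is unknown because the number affected is not given. If 5–15% of effectiveness patients are already responders at placement and 75% of them end as successes (both assumed), the error goes from 1.3% to 2.0–4.2% at n = 57 and from 1.9% to 2.7–5.0% at n = 43. The nominal 2.5% may or may not be exceeded. If all persist, the ceilings are 3.1–12.3% and 3.9–12.5%. This is an inexpensive improvement worth making; the sample size of 43 is not in error.

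**What to change.** In Sections 4.1 and 8.1.1 and the synopsis, tie the rule to the intervening procedure. For any patient who has ESWL or a plastic stent between the enrolment score and study stent placement:

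- use as baseline the last pain score taken after that procedure and before study stenting;
- apply the same re-check of criteria 6 and 7 for inclusion in the primary effectiveness analysis;
- report the result on the enrolment baseline as a sensitivity analysis.

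This also settles which score counts when a plastic stent is removed in an earlier session.

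The placement-visit score is already scheduled, so the change is mainly to wording. It has three costs or limits:

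- A few more patients may leave the effectiveness analysis.
- Where ESWL and study stenting share a session, a score taken beforehand cannot separate their effects.
- Pain is recalled since the prior visit (Section 7.4.1 and Appendix 22.5), so the new baseline may still include some pre-ESWL pain, as it may include pain from before the plastic stent in exchange patients.
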